5.1.1.1.4 Missing Data

General missing data handling conventions are summarized as follows:

- Missing data will not be imputed and all analyses will be based on observed data.
- Partial dates handling conventions are specified in Section 6.3, but will be listed in the data listings as they appear on the electronic case report forms (eCRFs).

5.1.1.2 Demographics

The safety population will be used to summarize demographics.

5.1.1.2.1 Analysis Populations

The distribution of patients within the analysis populations will be summarized as described in [Table 5-3](#).

Table 5-3 Analysis Population Summaries

Population	Description	Timing	Methodology
mITT and safety populations	Distribution in total and by treatment group	—	Categorical counts

5.1.1.2.2 Patient Disposition

Patient disposition encompasses the distribution of patients who enter, complete, and discontinue each specified analysis period, along with eCRF-reported discontinuation reasons from each respective analysis period. Patient disposition will be summarized as shown in [Table 5-4](#).

Table 5-4 Patient Disposition Summaries

Parameter	Description	Timing	Methodology
Study disposition	Distribution in total and by treatment group	During study	Categorical descriptives
Patient disposition ^a by phase	Distribution in the safety population in total and by treatment group	Treatment Period	Categorical descriptives

^a Patients who prematurely discontinued will be listed.

5.1.1.2.3 Protocol Deviations

Protocol deviations will be defined in a separate document, including importance classification. Protocol deviations will be summarized as shown in [Table 5-5](#).

Table 5-5 Protocol Deviation Summary

Parameter	Description	Timing	Methodology
Significant protocol deviations ^a	Distribution in the safety population in total and by treatment group	—	Categorical descriptives

^a Patients with significant protocol deviations will be listed.

5.1.1.2.4 Demographics

Demographics will be summarized in total and by treatment group for the safety population as shown in [Table 5-6](#).

Table 5-6 Demographic Summaries

Parameter	Description	Timing	Methodology
Age ^a	Age (years) relative to informed consent date	Informed consent	Continuous descriptives
Age group	
 • < 45 years • 45-65 years • > 65 years 	Informed consent	Categorical descriptives
Sex, and race ¹	
 • eCRF categories • Race group 1 
 ○ Caucasian ○ Black ○ Asian ○ Hispanic ○ Other • Race group 2 
 ○ Caucasian ○ Non-caucasian 	Screening period	Categorical descriptives

^a Patient demographics will be listed.

5.1.1.2.5 Medical History

Medical and ophthalmic history, encompassing abnormalities and surgeries reported as occurring before the Screening Visit, will be coded using the Medical Dictionary for Regulatory Activities (MedDRA), version 19.0 or newer. Unique patients who report medical history events will be summarized by MedDRA system organ class (SOC) and preferred term (PT) in total and by treatment group for the safety population as shown in [Table 5-7](#).

Table 5-7 Medical History Summary

Parameter	Description	Timing	Methodology
Medical history	Abnormalities and surgeries	Past	Categorical descriptives
Medical condition at trial initiation	Abnormalities and surgeries	Currently at the time informed consent was obtained	Categorical descriptives
Ophthalmic history	Ophthalmic abnormalities and surgeries	Past	Categorical descriptives
Ophthalmic condition at	Ophthalmic abnormalities and surgeries	Currently at the time	Categorical

Parameter	Description	Timing	Methodology
trial initiation		informed consent was obtained	descriptives

5.1.1.2.6 Prior and Concomitant Medications

Medications will be coded using the WHO Drug Dictionary Enhanced (DDE), version MAR2016 or newer. Unique patients who reported medications will be summarized by MedDRA SOC, and PT, and WHO DDE drug base preferred name in total and by treatment group for the safety population as shown in [Table 5-8](#).

Table 5-8 Medication Summaries

Parameter	Description	Timing	Methodology
Prior medications	Medications taken ≥ 1 time before the study treatment start date, regardless of medication end date	Screening period	Categorical descriptives
Concomitant medications	Medications taken ≥ 1 time on or after the study treatment start date, regardless of medication start date	Treatment period	Categorical descriptives

5.1.1.3 Exploratory Efficacy Analyses

5.1.1.3.1 Schirmer's Tear Test (With Anesthesia)

Schirmer's tear test (with anesthesia) will be summarized by treatment group as shown in [Table 5-9](#).

Table 5-9 Schirmer's Tear Test Summaries

Endpoint	Description	Timing	Methodology
Schirmer's tear test score ^a	Summary by analysis visit	Cycle 1: Study baseline (Day 1) and Weeks 4, 8, 12, and 24 Cycle 2: Cycle baseline and Weeks 4R, 8R, and 12R	CFB descriptives
Number (percent) of responders	Summary by analysis visit 
 Responder defined as ≥ 10 mm/5 min increase from study baseline in Schirmer's tear test score 	Cycle 1: Weeks 4, 8, 12, and 24	Categorical descriptives

^a All schirmer's tear test data will be listed.

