5.1.1.1.3 Statistical Methodology

The methodologies defined in Table 5-2 apply as specified to individual endpoints defined in this SAP for stage 1.

Table 5-2 Statistical Methodology – Stage 1

Methodology	Description
Categorical counts	
 • Number of patients in individual categories 
 ○ Patients with ≥ 1 qualifying event counted once per individual category
Categorical descriptives	
 • Number and percentage of patients in individual categories 
 ○ Patients with ≥ 1 qualifying event counted once per individual category • N1 if percentage denominator \neq number of patients in the population (standard percentage denominator) 
 ○ N1 = patients with nonmissing value
Continuous descriptives	
 • N1, mean, SD, median, minimum, maximum • N1 = patients with nonmissing value
CFB descriptives	
 • Continuous descriptives for baseline, postbaseline, and CFB values • N1 = patients with nonmissing values at both baseline and the specified postbaseline analysis visit
Responder	
 • Categorical descriptives for responders and nonresponders • N1 = patients with nonmissing values at both baseline and the specified postbaseline analysis visit

CFB = change from baseline

Two treatment cycles are defined in this analysis plan. Treatment Cycle 1 includes all visits from study baseline (also called cycle 1 baseline) to Week 24 or Exit visit if a patient receives ██████████ throughout the study, or to the last visit before retreatment if a patient receives ██████████ during the study. For visits in treatment Cycle 1, refer to study windows in Section 6.2. Treatment Cycle 2 applies to patients who receive retreatment, and includes all visits from retreatment and thereafter. Visits in treatment Cycle 2 will be determined based on the study days relative to the retreatment visit using the study windows specified in Section 6.2.

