5.1.1.3.6 Ocular Surface Disease Index

The Ocular Surface Disease Index (OSDI) Questionnaire consists of 12 questions based on which the total score (questions 1-12) and 3 subscales including ocular symptoms (questions 1-3), vision-related functioning (questions 4-9), and environmental triggers (questions 10-12) will be computed. The patients will be asked to rate each symptom using a 5-point scale (0 to 4), where 0 = none of the time, 1 = some of the time, 2 = half of the time, 3 = most of the time, and 4 = all of the time. Seven questions allow a response of not applicable (N/A). A higher score represents greater disability.

The OSDI Questionnaire scores will be summarized by treatment group as shown in [Table 5-14](#).

Table 5-14 Ocular Surface Disease Index Summaries

Endpoint	Description	Timing	Methodology
OSDI score ^a	Summary by analysis visit and by 
 The total OSDI score The 3 subscale scores (specified in Table 6-20) 	Cycle 1: Study baseline (Day 1) and Weeks 4, 12, and 24 Cycle 2: Cycle baseline and Weeks 4R and Week 12R	CFB descriptives
Number (percent) of responders	Summary by analysis visit 
 Responder is defined as ≥ 20 point decrease from study baseline in total OSDI score 	Cycle 1: Weeks 4, 12, and 24	Categorical descriptives

^a All ocular surface disease index data will be listed.

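### Both responder rows in the Stage 1 SAP cite the general categorical method, not the dedicated Responder method, leaving the percentage denominator open (minor)

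*SAP*

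**What the plan says.** SAP 5.1.1.1.3 (Table 5-2) sets out the summary methods that later tables cite by name. Two matter here.

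- *Categorical descriptives* reports numbers and percentages of patients. Its default denominator is the "number of patients in the population (standard percentage denominator"). If another denominator is used, an N1 of patients with an observed value is shown.
- *Responder* is described as "Categorical descriptives for responders and nonresponders", with "N1 = patients with nonmissing values at both baseline and the specified postbaseline analysis visit".

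The SAP has two responder endpoints. Table 5-9 (SAP 5.1.1.3.1) has the Schirmer row: "Responder defined as ≥ 10 mm/5 min increase from study baseline in" the test score, at Cycle 1 Weeks 4, 8, 12 and 24. Table 5-14 (SAP 5.1.1.3.6) has the OSDI row: "Responder is defined as ≥ 20 point decrease from study baseline in total OSDI score", at Cycle 1 Weeks 4, 12 and 24. Both name *Categorical descriptives* in the Methodology column. No table cites *Responder*.

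Two other provisions bear on the point. SAP 5.1.1.1.4 states: "Missing data will not be imputed and all analyses will be based on observed data". SAP 5.1.1.1.3 runs Cycle 1 to Week 24 or exit for patients who are not retreated, "or to the last visit before retreatment if a patient receives" retreatment. Later visits of a retreated patient belong to Cycle 2.

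**The concern.** The SAP contains a denominator rule written for responder endpoints, yet points both of those endpoints at a different method with a different default. Two programmers could follow the text in good faith and report different percentages.

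The gap matters because analysis-population membership does not guarantee a value at each visit. The mITT population (SAP Table 5-1) needs a baseline and one later assessment on any one exploratory efficacy measure. A member can therefore lack a Schirmer or OSDI value at a given visit. On the population denominator, that patient lowers the responder percentage just as an observed nonresponder would.

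Cohorts 6C and 6D are the clearest case. Protocol 5.10 plans their retreatment at Week 12, which ends Cycle 1 for each patient retreated. Both responder rows still list Cycle 1 Week 24 with no cohort qualifier, and neither has a Cycle 2 entry. Elsewhere the SAP does qualify Cycle 1 visits by cohort, for example Week 12 in the laboratory, vital-sign and IOP tables (5-19, 5-20 and 5-26). A 0% for a retreated cohort, printed beside real percentages for single-dose cohorts, would read as absence of response. SAP 5.1.1.7 says the Stage 1 analyses are meant to inform later study design.

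**Working it through.** **Inputs.** Cohort sizes come from SAP 5.1.2: 3 patients in Cohort 1; 4 in each of Cohorts 2, 6C and 6D; 8 in each of Cohorts 3, 4, 5A, 5B, 6A and 6B. The plan's own total reproduces: 3 + 3×4 + 6×8 = 63 patients in 10 cohorts. The documents state no responder rate and no missing-visit rate, so those figures below are assumptions, shown over a range.

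**Formulas.** With r responders, population size N and m patients without the value:

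- standard denominator of *Categorical descriptives*: r / N
- *Responder* method: r / N1, where N1 = N − m

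**Cohort of 8, assumed r = 3**

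| Missing (m) | r / N | r / N1 | Difference (percentage points) |
|---|---|---|---|
| 0 | 3/8 = 37.5% | 3/8 = 37.5% | 0 |
| 1 | 3/8 = 37.5% | 3/7 = 42.9% | 5.4 |
| 2 | 3/8 = 37.5% | 3/6 = 50.0% | 12.5 |
| 3 | 3/8 = 37.5% | 3/5 = 60.0% | 22.5 |

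**Cohort 6C or 6D (N = 4) at Cycle 1 Week 24**

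| Patients retreated | Responders among those not retreated | r / N | r / N1 |
|---|---|---|---|
| 4 | none possible | 0/4 = 0% | N1 = 0, no percentage |
| 3 | 1 of 1 (assumed) | 1/4 = 25% | 1/1 = 100% |

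The second row is possible because Protocol 5.10 lets the investigator elect not to retreat. Such a patient stays in Cycle 1 to Week 24. It also shows why N1 must be printed: 100% means little unless the reader sees that it rests on one patient.

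**Consistency within Table 5-9.** The change-from-baseline row for the Schirmer score uses a method whose N1 already requires both baseline and visit values. At Week 24 a fully retreated cohort would show N1 = 0 in that row. On the standard denominator, the responder row of the same table would show 0/4.

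**The case against.** The strongest reply is that the cited method already contains the right answer. *Categorical descriptives* provides for an N1 of observed patients. Responder status is defined by change from study baseline, so it is observed only when both values exist. The N1 under either method is then the same set of patients, and *Responder* is by its own description a special case of the cited method. The observed-data rule in 5.1.1.1.4 favours N1 as well. Table layouts are specified in a separate document (SAP section 4), which may already cover N1 and empty cells. All Schirmer and OSDI data will be listed, so the denominator can be recovered patient by patient.

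Most of this stands. A reader might infer from the citation that the SAP orders missing visits to be counted as failures, or that a false 0% will certainly be printed for 6C and 6D. The documents do not support either reading.

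What the reply does not do is close the gap. The N1 clause says what to show when the denominator differs from the population; it does not say when it should differ. The observed-data rule bars imputation, but a programmer who divides observed responders by the population has imputed no value and could think the rule was met. The *Responder* line settles the denominator explicitly, and it is the line that is not cited. Whether the separate specification document resolves this cannot be seen from the SAP.

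**Conclusion.** The method citation is wrong in both responder rows, and the denominator is left unresolved as a result. The consequences are conditional: they follow only if the standard population denominator is applied.

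In that case the difference for a cohort of 8 with 3 responders is 5.4 to 22.5 percentage points for 1 to 3 missing visits, all assumed counts. A 6C or 6D cohort in which all 4 patients are retreated would show 0% at Cycle 1 Week 24 where no patient can be evaluated. The 0/4 result assumes all 4 are in the analysis population and all are actually retreated.

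The impact is minor. The endpoints are exploratory, the summaries are descriptive, no test is specified on responder rates, and the sample size is empirical. The correction is still worth making because, with 3 to 8 patients per cohort, a single missing visit visibly moves a percentage.

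**What to change.** In the responder rows of SAP Tables 5-9 and 5-14:

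1. Change the Methodology entry from *Categorical descriptives* to *Responder*.
2. Print N1 with each percentage, and show 'not evaluable' where N1 = 0.
3. Add a note that retreated patients have no Cycle 1 Week 24 value and so do not enter that denominator.

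The cost is two table cells and one note in the SAP, with a matching check of the table specification document. No new data are needed, and the method is already defined in Table 5-2.

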5.1.1.3.2 Tear Film Break-Up Time

Tear film break-up time (TBUT) will be summarized by treatment group as shown in [Table 5-10](#).

Table 5-10 Tear Film Break-Up Time Summaries

Endpoint	Description	Timing	Methodology
TBUT	Summary by analysis visit 
 The average value of 3 measurements in each eye at each visit will be used 	Cycle 1: Study baseline (Day 1) and Weeks 4, 8, 12, and 24 Cycle 2: Cycle baseline and Weeks 4R, 8R, and 12R	CFB descriptives

5.1.1.3.3 Sodium Fluorescein Corneal Staining

Sodium fluorescein corneal staining will be summarized by treatment group as shown in [Table 5-11](#).

Table 5-11 Sodium Fluorescein Corneal Staining Summaries

Endpoint	Description	Timing	Methodology
CFB in ordinal scale	Summary by analysis visit	Cycle 1: Study baseline (Day 1) and Weeks 4, 8, 12, and 24 Cycle 2: Cycle baseline and Weeks 4R, 8R, and 12R	CFB descriptives

5.1.1.3.4 Lissamine Green Conjunctival Staining

Lissamine green conjunctival staining will be summarized by treatment group as shown in [Table 5-12](#).

Table 5-12 Lissamine Green Conjunctival Staining Summaries

Endpoint	Description	Timing	Methodology
CFB in ordinal scale of conjunctival staining	Summary by analysis visit and by area (nasal, temporal) and in total 
 Total is calculated as the sum of areas – nasal and temporal 	Cycle 1: Study baseline (Day 1) and Weeks 4, 8, 12, and 24 Cycle 2: Cycle baseline and Weeks 4R, 8R, and 12R	CFB descriptives

Endpoint	Description	Timing	Methodology
CFB in ordinal scale of total corneal and conjunctival staining	Summary by analysis visit 
 Total corneal and conjunctival staining is the sum of corneal staining plus conjunctival staining (nasal plus temporal) 	Cycle 1: Study baseline (Day 1) and Weeks 4, 8, 12, and 24 Cycle 2: Cycle baseline and Weeks 4R, 8R, and 12R	CFB descriptives

5.1.1.3.5 Patient Symptoms (Visual Analog Scale)

A short questionnaire utilizing a VAS to quantify the severity of symptoms of dry eye will be administered. The questions refer to TODAY only including overall ocular discomfort from dry eye disease, level of discomfort experienced from symptoms as specified in [Table 6-18](#). The score will be 0 to 100 with 0 = none and 100 = extreme.

Patient symptoms (VAS) will be summarized by treatment group as shown in [Table 5-13](#).

Table 5-13 Patient Symptoms (Visual Analog Scale) Summaries

Endpoint	Description	Timing	Methodology
Overall VAS score ^a	Summary by analysis visit	Cycle 1: Study baseline (Day 1) and Weeks 12 and 24 Cycle 2: Cycle baseline and Weeks 8R and 12R	CFB descriptives
Worse VAS score ^a	Summary by analysis visit 
 For each patient, the symptom among all 9 symptoms (specified in Table 6-18) with the worst VAS at baseline (Day 1) will be used. If no single symptom can be identified at baseline (Day 1), the symptom with the worst VAS score at screening will be used. 	Cycle 1: Study baseline (Day 1) and Weeks 12 and 24 Cycle 2: Cycle baseline and Weeks 8R and 12R	CFB descriptives

^a All patient symptoms (VAS) data will be listed.

5.1.1.3.6 Ocular Surface Disease Index

The Ocular Surface Disease Index (OSDI) Questionnaire consists of 12 questions based on which the total score (questions 1-12) and 3 subscales including ocular symptoms (questions 1-3), vision-related functioning (questions 4-9), and environmental triggers (questions 10-12) will be computed. The patients will be asked to rate each symptom using a 5-point scale (0 to 4), where 0 = none of the time, 1 = some of the time, 2 = half of the time, 3 = most of the time, and 4 = all of the time. Seven questions allow a response of not applicable (N/A). A higher score represents greater disability.

The OSDI Questionnaire scores will be summarized by treatment group as shown in [Table 5-14](#).

Table 5-14 Ocular Surface Disease Index Summaries

Endpoint	Description	Timing	Methodology
OSDI score ^a	Summary by analysis visit and by 
 The total OSDI score The 3 subscale scores (specified in Table 6-20) 	Cycle 1: Study baseline (Day 1) and Weeks 4, 12, and 24 Cycle 2: Cycle baseline and Weeks 4R and Week 12R	CFB descriptives
Number (percent) of responders	Summary by analysis visit 
 Responder is defined as ≥ 20 point decrease from study baseline in total OSDI score 	Cycle 1: Weeks 4, 12, and 24	Categorical descriptives

^a All ocular surface disease index data will be listed.

5.1.1.3.7 Treatment Assessment by Investigator

The follow-up investigator will complete a global evaluation of the overall effect of investigational medication administered in reference to the Baseline visit (Day 1) prior to the [REDACTED] of the investigational medication for each eye at the scheduled visits. The global evaluation score will be assessed based on the following scale:

- 0 = Completely cleared, no sign or symptom of disease
- 1 = Almost cleared: very significant clearance in disease with only traces of active disease remaining (approximately 90% improvement)
- 2 = Marked response: significant improvement with some disease remaining (approximately 75% improvement)
- 3 = Moderate response: intermediate improvement, between slight and marked (approximately 50% improvement)
- 4 = Slight response: some improvement in disease state but significant disease remains (approximately 25% improvement)
- 5 = Condition unchanged
- 6 = Condition worsened

Treatment assessment by investigator will be summarized by treatment group as shown in [Table 5-15](#).

Table 5-15 Treatment Assessment by Investigator Summaries

Endpoint	Description	Timing	Methodology
Global evaluation score	Summary by analysis visit for the raw score	Cycle 1: Weeks 8, 12, and 24 Cycle 2: Week 8R, and Week 12R	Continuous descriptives

5.1.1.4 Safety Analyses

Safety analyses will be based on the safety population.

5.1.1.4.1 Study Treatment Exposure

Study treatment exposure and compliance will be summarized by treatment group for the safety population as shown in [Table 5-16](#).

Table 5-16 Study Treatment Summaries

Parameter	Description	Timing	Methodology
Study treatment exposure (days)	Date of study exit – date of 1st injection + 1	Treatment period	Continuous descriptives

5.1.1.4.2 Adverse Events

Adverse events (AEs) are defined as shown in [Table 5-17](#).

Table 5-17 AE Terms

Term	Description
TEAE	An adverse event recorded on the eCRF would be considered treatment-emergent if either of the following conditions are met: AE onset date \geq first study treatment date; or AE onset date $<$ first study treatment date and either: 
 • the severity of the event worsened on or after the first study treatment date, or • the event became serious on or after the first study treatment date
SeriousTEAE	An event identified as TEAE that further meets SAE criteria at any time would be a serious TEAE.

SAE = serious adverse event; TEAE = treatment-emergent adverse event

AEs, encompassing abnormalities and surgeries reported as occurring after the Screening Visit, will be coded using MedDRA version 19.0 or newer. Unique patients reporting AEs in the following AE categories will be summarized by treatment group for the safety population as shown in [Table 5-18](#).

Table 5-18 AE Summaries

Parameter	Description	Timing	Methodology
Overall summary	Overall summary for the following categories: 
 • TEAEs (ocular vs. non-ocular) • Study drug-related TEAEs (ocular vs. non-ocular) • Study procedure-related TEAEs (ocular vs. non-ocular) • Serious TEAEs (ocular vs. non-ocular) • TEAEs leading to study 	From treatment start date until Week 24/Week 12R or early termination date, whichever comes first	Categorical descriptives

Parameter	Description	Timing	Methodology
	
discontinuation (ocular vs. non-ocular)
 
 Deaths 		
TEAEs ^a	
Overall summary and by SOC in alphabetical order, PT and worst severity
 
The worst severity is defined as the greater of the onset severity and maximum severity following onset recorded on the eCRF. If the same TEAE term has been reported more than once for a subject with different severity grades, the worst severity grade will be used in the tabulation.
	
From treatment start date until Week 24/Week 12R or early termination date, whichever comes first
	Categorical descriptives
Ocular TEAEs	
Overall summary and by SOC in alphabetical order, PT and worst severity
 
The worst severity is defined as the greater of the onset severity and maximum severity following onset recorded on the eCRF. If the same TEAE term has been reported more than once for a subject with different severity grades, the worst severity grade will be used in the tabulation.
	
From treatment start date until Week 24/Week 12R or early termination date, whichever comes first
	Categorical descriptives
Study drug-related ocular TEAEs	
Overall summary and by SOC in alphabetical order and PT
	
From treatment start date until Week 24/Week 12R or early termination date, whichever comes first
	Categorical descriptives
Study procedure-related ocular TEAEs	
Overall summary and by SOC in alphabetical order and PT
	
From treatment start date until Week 24/Week 12R or early termination date, whichever comes first
	Categorical descriptives
Serious TEAEs	
Overall summary and by SOC in alphabetical order and PT
	
From treatment start date until Week 24/Week 12R or early termination date, whichever comes first
	Categorical descriptives
TEAEs leading to study discontinuation	
Overall summary and by SOC in alphabetical order and PT
	
From treatment start date until Week 24/Week 12R or early termination date, whichever comes first
	Categorical descriptives

eCRF = electronic case report form; PT = preferred term; SAE = serious adverse event; SOC = system organ class;
TEAE = treatment-emergent adverse event

^a All AEs including pretreatment AEs and TEAEs, and SAEs will be listed.

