7.3.1 Safety Analyses

Safety measures will be analyzed using the safety population. The Medical Dictionary for Regulatory Activities (MedDRA) nomenclature will be used to code adverse events. The number and percentage of patients with treatment-emergent adverse events will be summarized. The adverse events will be classified into ocular and nonocular types and will be summarized separately. Detailed methods for the analyses of adverse events and other safety variables will be described in the SAP.

[REDACTED]

[REDACTED]

Approval Date: 19-Jan-2017

[Redacted]

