5.1.1 Statistical and Analytical Plans

5.1.1.1 Common Conventions

5.1.1.1.1 Analysis Populations

The analysis populations will consist of patients as defined in [Table 5-1](#).

Table 5-1 Analysis Populations – Stage 1

Population	Definition	Study Treatment
Safety	All patients who are treated	Actual received ^a
Modified intent-to-treat (mITT)	All randomized patients who have baseline and at least 1 postbaseline assessment for 1 or more of the exploratory efficacy measurements	Randomized assignment

^a Patients will be summarized according to the first study treatment received or study treatment received for majority of treatment period.

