The study baseline value of an assessment will be the measurement prior to the treatment at Day 1 unless it is missing. In that case, the last nonmissing value recorded prior to the treatment (Day 1) will be used instead. The cycle baseline (also called cycle 2 baseline) value of an assessment will be the measurement prior to the retreatment at Week 12 from the first treatment unless it is missing. In that case, the last nonmissing value recorded prior to the retreatment (Week 12) will be used instead.

Ocular evaluation will be summarized by study eye and contralateral eye separately.

Some raw and derived data listings will be provided, and will be fully defined in the table, figure, and data listing specification document.

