The macroscopic (gross) bulbar hyperemia grading consists of global assessments and regional assessments, which will be done under consistent illumination by comparing the appearance of the bulbar conjunctiva to standard photographs (Allergan bulbar conjunctival hyperemia grading guide) at the scheduled visits. Regional assessment includes superior temporal, superior nasal, inferior temporal, and inferior nasal assessment. It will be graded using a 5-point scale described as follows:

0	(None)	=	Normal; vessels of bulbar conjunctiva easily observed
+0.5	(Trace)	=	Trace flush, reddish-pink color
+1	(Mild)	=	Mild flush, reddish color
+2	(Moderate)	=	Bright red color
+3	(Severe)	=	Deep, bright diffuse redness

Macroscopic bulbar hyperemia will be summarized by treatment group for the safety population as shown in [Table 5-22](#).

Table 5-22 Macroscopic Bulbar Hyperemia Summaries

Endpoint	Description	Timing	Methodology
Global assessment: severity grade	Summary by analysis visit	Cycle 1: Study baseline (Day 1), Day 2, and Weeks 1, 2, 4, 8, 12, and 24 Cycle 2: Cycle baseline, Day 1R, and Weeks 1R, 4R, 8R, and 12R	Categorical descriptives

5.1.1.4.5.3 Slit-lamp Biomicroscopy

Slit-lamp biomicroscopy will be summarized by treatment group for the safety population. Biomicroscopy findings will be coded using MedDRA terminology and summarized for each eye by treatment group as shown in [Table 5-23](#).

Table 5-23 Slit-lamp Biomicroscopy Summaries

Endpoint	Description	Timing	Methodology
One or more severity grade increase from baseline	Overall summary and by PT	From treatment start date until Week 24/Week 12R or early termination date, whichever comes first	Categorical descriptives

PT = preferred term

5.1.1.4.5.4 Dilated Ophthalmic Examinations

Ophthalmoscopy findings will be coded using MedDRA terminology.

Cup/disc ratio will be reported using a 0.0 to 1.0 scale. The Armaly chart provided by Allergan provides a pictorial scale of cup/disc ratio of 0.0 to 0.8. Only listing will be provided for cup/disc ratio.

Dilated ophthalmic examinations will be summarized by treatment group for the safety population as shown in [Table 5-24](#).

Table 5-24 Dilated Ophthalmic Examinations Summaries

Endpoint	Description	Timing	Methodology
One or more severity grade increase from baseline	Overall summary and by PT	Week 12 (for Cohorts 6C and 6D only), Week 24/Week 12R or early termination date, whichever comes first	Categorical descriptives

PT = preferred term

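### SAP Table 5-18 counts ocular TEAEs by patient and grades them per subject, although Stage 1 randomises the eye; run as written, it cannot show the study-eye versus contralateral-eye contrast

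*SAP*

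**What the plan says.** SAP 4.1 and Protocol 5.4 randomise the right or left eye to F1 or F2, with vehicle in the fellow eye. In Cohort 1 the pair is vehicle and sham.

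SAP 5.1.1.4.2 sets the unit for all adverse event tables: "Unique patients reporting AEs in the following AE categories will be summarized by treatment group for the safety population". The method named in Table 5-18 is defined in Table 5-2: "Patients with ≥ 1 qualifying event counted once per individual category". The treatment groups in SAP 5.1.1.1.2 are the cohorts, and no separate group is defined for vehicle-treated fellow eyes. The ocular TEAE row of Table 5-18 has a severity rule that begins "If the same TEAE term has been reported more than once for a subject with different severity grades" and then takes the worst grade. The same rule appears in the row for all TEAEs.

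Two statements elsewhere bear on the eye. The general methodology section, SAP 5.1.1.1.3, says: "Ocular evaluation will be summarized by study eye and contralateral eye separately". The slit-lamp section, SAP 5.1.1.4.5.3, says: "Biomicroscopy findings will be coded using MedDRA terminology and summarized for each eye by treatment group". Neither SAP 5.1.1.4.2 nor Table 5-18 mentions either eye.

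Protocol 7.3.1 asks for a patient count, "The number and percentage of patients with treatment-emergent adverse events will be summarized", and hands over the rest: "Detailed methods for the analyses of adverse events and other safety variables will be described in the SAP".

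**The concern.** Safety is the first-named Stage 1 objective. In Cohorts 2 onward, the randomised comparison for local reactions is the drug eye against the vehicle eye of the same patient. A table that counts a patient once, whichever eye was affected, places vehicle-eye events under the cohort's heading and loses that comparison. This affects three sets of rows: all ocular TEAEs, drug-related ocular TEAEs and procedure-related ocular TEAEs.

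The severity rule adds a second loss. If a patient has a mild event in one eye and a severe event of the same term in the other, the table shows one severe event and does not say which eye had it.

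Other outputs offset this only in part. The slit-lamp summary is by eye, but symptoms such as pain are not among the conditions in Table 6-24. The supplemental questionnaire asks about pain in each eye (Table 6-26), but the only endpoint that Table 5-28 lists for summary is treatment satisfaction. The adverse event listings hold the data but do not summarise them.

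**Working it through.** **Cohort sizes.** SAP 5.1.2 gives 3 patients in Cohort 1, 4 in each of Cohorts 2, 6C and 6D, and 8 in each of Cohorts 3 through 6B (3, 4, 5A, 5B, 6A, 6B). The sum is 3 + 3×4 + 6×8 = 63, which matches the stated maximum. The sample size is empirical, so there is no power or alpha calculation to reproduce.

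**What a patient-level cell leaves open.** Suppose k of n patients in a cohort have a given ocular TEAE in at least one eye. Let a be the number with it in the study eye and c the number with it in the contralateral eye. Then

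- a ≤ k and c ≤ k, because only these k patients are affected;
- a + c ≥ k, because each of them is affected in at least one eye.

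The number of pairs (a, c) that fit is (k+1)(k+2)/2. Every patient contributes one eye of each kind, so both eyes have denominator n, and the difference (a − c)/n runs from −k/n to +k/n.

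| n | k | Pairs that fit | Range of difference (percentage points) |
|---|---|---|---|
| 8 | 1 | 2×3/2 = 3 | ±12.5 |
| 8 | 2 | 3×4/2 = 6 | ±25 |
| 8 | 3 | 4×5/2 = 10 | ±37.5 |
| 4 | 1 | 2×3/2 = 3 | ±25 |

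For example, three patients affected only in the study eye and three affected only in the contralateral eye both give a cell of 3/8. By eye, the first is 3/8 against 0/8 and the second is 0/8 against 3/8.

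The values of k are illustrative, because the documents give no event rates. The ranges assume nothing about rates or about dependence between the two eyes. They follow from any count that pools two eyes, and they apply only if the table is run as written.

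**Does the general convention resolve it?** Set beside Table 5-18, SAP 5.1.1.1.3 speaks of ocular evaluation and does not name adverse events, and SAP 5.1.1.4.2 does not refer to it. The nearest comparable output, the MedDRA-coded slit-lamp summary, states the split by eye in its own section. If the convention does apply, it separates the counts. It still does not change a severity rule written per subject, and it does not say how a bilateral event is counted.

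**The case against.** The strongest reply is that the rule already exists. SAP 5.1.1.1.3 is part of the common conventions and can be read as covering every ocular summary. The Schirmer, TBUT, corneal staining and global hyperemia sections are also written by treatment group without restating the split by eye, so silence in the adverse event section proves little. Patient wording does not imply pooling either: Table 5-2 defines all categorical summaries as counts of patients, and BCVA line change, an eye-level measure, uses the same method. The severity sentence is identical in the all-TEAE and ocular rows, which suggests standard text more than a decision to merge the eyes. Table specifications are in a separate document (SAP 4), which may already show one panel per eye.

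Much of this stands. A reader might infer that the SAP has no by-eye rule, or that it has chosen to pool the eyes for adverse events. The documents support neither. Two other possible supports are weak. The footnote to Table 5-1, "Patients will be summarized according to the first study treatment received or study treatment received for majority of treatment period", is naturally read as dealing with patients whose treatment differed from plan, not with how eyes are tabulated. The cohort labels in SAP 5.1.1.1.2 are partly redacted, so little can be built on their wording. The Amendment 5 summary has wording that groups ocular adverse events with other ocular evaluations. It describes superseded text and is not in the current Protocol 7.3.1, so it does not settle the point.

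The reply does not remove two things: the convention's reach to adverse events is left to inference, and the severity rule stays per subject even on the favourable reading.

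**Conclusion.** The point holds as a cheap improvement. As written, Table 5-18 counts patients by cohort and assigns one grade per subject, while the randomised unit is the eye. Run that way, the ocular TEAE rows cannot show the within-patient contrast, and a bilateral event carries one grade across two differently treated eyes. If SAP 5.1.1.1.3 or the table specifications already split the counts, the remaining gap is the within-eye severity rule and the counting of bilateral events.

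No stated figure, test or decision rule changes, so nothing here shows that a Stage 1 safety conclusion would be wrong. The size depends on event counts that the documents do not give. The listings and the other by-eye summaries soften the loss. The any-eye patient count is legitimate, since it is what Protocol 7.3.1 asks for.

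**What to change.** In Table 5-18, state that the three sets of ocular TEAE rows (all, drug-related, procedure-related) are tabulated within cohort separately for study eye and contralateral eye. Take worst severity within eye, and count a bilateral event once in each eye. Keep an any-eye patient row, so that the protocol's patient count is still reported, and keep the patient as the unit for nonocular events.

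If SAP 5.1.1.1.3 was already meant to cover ocular TEAEs, a cross-reference plus the rules for within-eye severity and bilateral events is enough.

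The cost is one or two sentences in the SAP, matching table shells and slightly larger tables. It assumes that the eCRF records the eye for each ocular event, which should be confirmed first.
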